## Study Design

The planned pilot study is a prospective study to compare the use of exercises augmented with BFR with quantitative measurements of strength and patient reported outcomes. A total of 33 youth and adolescent patients undergoing a surgical procedure for ACL reconstruction at Connecticut Children's Elite Sports Medicine and completing physical therapy at Connecticut Children's Sports Physical Therapy will be recruited for this study. Additionally, 14 patients will be recruited that do not participate at Connecticut Children's Sports Physical Therapy and do not receive BFR training as prospective controls. Should we be unable to obtain 20 prospective controls, a review of data from 20 previous patients, matched for age, sex, BMI and surgical procedure that completed physical therapy at Connecticut Children's Sports Physical Therapy will be used as a comparison.

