## Data Analysis:

The endpoint of this study is when data is collected and analyzed from 20 patients who have completed a one year follow up from date of surgery.

Data will be collected on all patients who meet the inclusion criteria for this study and have agreed to participate through the consenting process. Descriptive statistics will be completed to help gain an overall understanding of the data for the effect of BFR training on lower extremity strength, mid-thigh circumference and outcome measures. T-tests between strength and outcome variables for the BFR and non-BFR group to test if there are differences between the two groups. Correlation tests will be used to determine association between lower extremity strength and BFR training. Corrections will be made for multiple comparisons.

We will be entering into a Data Use Agreement with University of Connecticut (UCONN) for assistance with data analysis and interpretation as well as statistical analysis. All data sharing procedures will be in accordance with Connecticut Children's policy. All data will be de-identified prior to sharing to assure patient's confidentiality. The UCONN collaborator is not engaged in human subject research (no access to identifiers) and will obtain an independent determination from the UCONN IRB.

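### If the matched retrospective controls are used, the planned t-test, as most naturally read, ignores the matching factors; a linear model that includes them would recover any lost precision at little cost

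*Combined protocol and SAP*

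**What the plan says.** The Study Design section plans a BFR group ("A total of 33 youth and adolescent patients undergoing a surgical procedure for ACL reconstruction") and a smaller prospective control group treated elsewhere ("Additionally, 14 patients will be recruited that do not participate at Connecticut Children's Sports Physical Therapy"). It then gives a fallback: "Should we be unable to obtain 20 prospective controls, a review of data from 20 previous patients", who are to be "matched for age, sex, BMI and surgical procedure", will serve as the comparison. It does not say whether matching is patient to patient or only at group level, and it gives no ratio.

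The Data Analysis section names one method for comparing groups: "T-tests between strength and outcome variables for the BFR and non-BFR group to test if there are differences between the two groups". It adds descriptive statistics, correlation tests and the sentence "Corrections will be made for multiple comparisons". It mentions no paired test, no matched-set term and no adjustment for any covariate.

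**The concern.** Matching on factors that predict the outcome makes the outcomes of matched patients positively correlated. A two-sample t-test assumes independent groups. It therefore leaves the variation due to the matching factors in its standard error, although the matching has removed part of that variation from the difference in means. Confidence intervals are then wider than they need to be and p-values too large. The Study Limitations section already lists small sample size as a limit on power, so avoidable loss of precision matters here.

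The fallback is not a remote possibility. The target is 14 prospective controls, but the condition for using previous patients is failure to obtain 20. As written, a study that exactly meets its own target still meets that condition.

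**Working it through.** The documents state no alpha, power, effect size, standard deviation or within-pair correlation, so there is no planned figure to reproduce.

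**Inputs from the plan (Study Design):** 33 BFR patients; 20 matched previous patients.

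**Assumptions:** outcome SD of 1 in both groups; two-sided 5% for a single test, before any multiplicity correction; true difference of 0.6 SD for power; within-pair correlation ρ from 0 to 0.5; 20 of the 33 BFR patients each matched to one control.

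**1. Standard error.** The t-test uses variance 1/33 + 1/20 = 0.0303 + 0.0500 = 0.0803, so SE = 0.2834. With 20 matched pairs, the covariance of the two group means is 20ρ/(33 × 20) = ρ/33, so the true variance is 0.0803 − 2ρ/33. The true type I error is approximately P(|t| > 2.008 × SE ratio) on 51 degrees of freedom.

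| ρ | true variance | t-test SE / true SE | type I error |
|---|---|---|---|
| 0 | 0.0803 | 1.00 | 5.0% |
| 0.1 | 0.0742 | 1.04 | 4.2% |
| 0.2 | 0.0682 | 1.09 | 3.4% |
| 0.3 | 0.0621 | 1.14 | 2.7% |
| 0.5 | 0.0500 | 1.27 | 1.4% |

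**2. Other group sizes.** On a fully matched 20 v 20 set the ratio is 1/√(1 − ρ): 1.12 at ρ = 0.2 and 1.41 at ρ = 0.5. If the 14 prospective controls are pooled with the 20, giving 33 v 34, the t-test variance is 1/33 + 1/34 = 0.0597 and the covariance term is 2 × 20ρ/(33 × 34) = 0.0357ρ. At ρ = 0.5 the ratio is √(0.0597/0.0419) = 1.19.

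**3. Power with adjustment, 33 v 20, difference 0.6 SD.** Unadjusted: 0.6/0.2834 = 2.12 on 51 degrees of freedom, about 55%. A linear model with the four factors has SE = 0.2834 × √(1 − R²) on about 47 degrees of freedom, where R² is the share of outcome variance that the factors explain.

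| R² | SE | power |
|---|---|---|
| 0 | 0.283 | 54.5% |
| 0.1 | 0.269 | 59% |
| 0.2 | 0.253 | 64% |
| 0.3 | 0.237 | 70% |

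This takes one degree of freedom per factor and groups roughly balanced on the factors. If the factors explain nothing, the cost is 54.7% − 54.5% = 0.2 points.

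**4. Power of a 1:1 paired t-test.** This uses 20 pairs and drops 33 − 20 = 13 BFR patients. SE = √(2(1 − ρ)/20) on 19 degrees of freedom. Power at 0.6 SD is 44% at ρ = 0, 48% at 0.1, 52% at 0.2, 55% at 0.25 and 72% at 0.5. It matches the 55% of the unpaired 33 v 20 test only at ρ of about 0.25.

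**The case against.** **The test is not declared to be unpaired.** True: the plan is silent, and a paired t-test is also a t-test. But a test for differences between two groups is ordinarily the two-sample test, and no pairs are defined. If a paired test was meant, the text still has to say so.

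**A reader might infer a planned 20 v 20 matched set.** The end of the study is defined by data "from 20 patients who have completed a one year follow up from date of surgery", and 20 previous patients are the fallback. The documents do not support that inference. The 20 in the Data Analysis section carry no group label. The Study Design section plans 33 BFR patients, and the Sample Size Justification intends to use every eligible patient. The data-collection list speaks of three groups, so unmatched prospective controls may sit beside the matched ones. The 12% to 41% inflation that a 20 v 20 set gives for ρ of 0.2 to 0.5 should therefore not be quoted as the plan's own case.

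**The correlation may be near zero.** This stands. With close matching, ρ is roughly the share of outcome variance that the factors explain. The strength deficits are ratios of the involved to the uninvolved side within a patient, which may already remove much of the effect of body size. Ages run only from 12 to 18, and the Study Limitations section expects mostly one surgeon and one graft type. Repetition counts and patient-reported scores are not all such ratios, so the argument does not cover every outcome.

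**The error is conservative, and this is a pilot.** Also true. Ignoring the matching does not by itself bias the estimated difference, and matching still helps comparability. That limits the seriousness of the point but does not argue against a change of wording.

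**Conclusion.** The point holds conditionally. If the matched previous patients are used, and if the four factors predict the outcome, the t-test as most naturally read overstates the standard error and loses power. On 33 v 20 with 20 matched, the overstatement is 0% to 27% for assumed correlations of 0 to 0.5, with type I error between 5% and about 1.4%. The size depends on a correlation that the documents do not give, and it may be small for the strength deficits.

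A reader might go further and conclude that the intervals and p-values will certainly be wrong, or that a paired t-test is required. Neither follows: at ρ = 0 there is no error, and below about 0.25 the paired test on 20 pairs has less power than the plain test on all 33 v 20. This is a cheap improvement, not a flaw that undermines the study.

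**What to change.** In the Data Analysis section, replace the bare t-test with a linear model of each outcome on BFR group, age, sex, BMI and surgical procedure, keeping all BFR patients. If matching is individual, add a matched-set effect, for example as a random effect in a mixed model. In the Study Design section, state whether matching is individual or at group level and at what ratio. Also reconcile the 14 and the 20 prospective controls, and say whether prospective and retrospective controls are pooled. Do not restrict the comparison to 1:1 pairs.

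The cost is about four degrees of freedom (more if surgical procedure has several categories) and slightly more analysis work. The data list already collects age, sex, BMI and surgical details, and matching the previous patients requires the same items. Because the comparison is not randomised, the model also adjusts for imbalance in these four factors among patients who are not matched.

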## **Target Population**

The target population for this study consists of patients post ACL Reconstruction whom have been treated and followed by Elite Sports Medicine at Connecticut Children's and completed physical therapy at Connecticut Children's Sports Physical Therapy. The inclusion and exclusion criteria will be the same for both the study and control groups.

## **Study Group Inclusion criteria**:

- Patients between the age of 12 and 18 years at the time of surgery.
- Post-primary ACL reconstruction
- Orthopaedic surgical intervention (including all additional procedures at the knee) completed by one of the Elite Sports Medicine physicians.
- Patient completed postoperative rehabilitation following standard protocols
- No contraindications to performing BFR, as outlined in the Owens Recovery [18] Science 2018 Personal Blood Flow Restriction manual.

### **Prospective Control Inclusion Criteria:**

- Patients between the age of 12 and 18 years at the time of surgery.
- Post-primary ACL reconstruction
- Orthopaedic surgical intervention (including all additional procedures at the knee) completed by one of the Elite Sports Medicine physicians.
- Patient completed postoperative rehabilitation following standard protocols
- Patient did NOT use BFR training during their rehabilitation
- Patient did NOT complete physical therapy at Connecticut Children's Sports Physical Therapy.

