- 6. 12-month testing

Tegner Activity Scale

- 7. Prospective control: All prospective controls will follow the ACL reconstruction protocol at an outside facility. These patients will complete outcome measures, and standardized strength assessments consistent with the standard current standard of care listed above. The same data points will be collected.
- 8. Retrospective controls: Outcome measures (RSI, IKDC) and the results of standardized 3 and 6mo + assessment results will be collected.
- 9. All data points listed above for all three groups will be stored in a Microsoft Excel spreadsheet on the G drive.

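### The prospective comparison estimates BFR plus clinic, and the plan is inconsistent about the same-clinic controls and about whether eligibility is the same in both groups

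*Combined protocol and SAP*

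**What the plan says.** **Groups.** Study Design describes the BFR group as "A total of 33 youth and adolescent patients undergoing a surgical procedure for ACL reconstruction" and "completing physical therapy at Connecticut Children's Sports Physical Therapy will be recruited for this study". For the comparison, "14 patients will be recruited that do not participate at Connecticut Children's Sports Physical Therapy and do not receive BFR training as prospective controls". The Prospective Control Inclusion Criteria repeat both conditions: no BFR, and "Patient did NOT complete physical therapy at" the in-house clinic. Item 7 of the data-collection list places these controls at an outside facility.

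**Same-clinic controls.** Study Design continues: "Should we be unable to obtain 20 prospective controls, a review of data from 20 previous patients", matched for age, sex, BMI and surgical procedure and treated at the in-house clinic, will serve as a comparison. Under Identification and Recruitment they come from a billing run covering January 2017 to January 2019, with no condition attached. Item 8 of the data-collection list says that RSI, IKDC and "the results of standardized 3 and 6mo + assessment results will be collected", again without condition, and item 9 speaks of three groups. Background says that BFR has been in consistent use at the in-house clinic since early 2019.

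**Eligibility.** Target Population says "The inclusion and exclusion criteria will be the same for both the study and control groups" and describes the population as having completed therapy in-house. The Study Group Inclusion criteria contain "No contraindications to performing BFR"; the prospective control list does not.

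**Analysis.** Data Analysis plans t-tests between the BFR and the non-BFR group, plus correlations, with an unspecified correction for multiple comparisons. No clinic term is mentioned. Study Limitations names sampling bias, lack of blinding, small sample, and a likely single surgeon and graft type.

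**The concern.** Nobody in the prospective comparison received BFR outside the in-house clinic, and nobody there went without it. Therapists, supervision, visit patterns and delivery of the rest of the programme may differ between the in-house clinic and outside facilities, and any such difference enters the BFR estimate in full. No covariate adjustment within those two groups can remove it. The stated use of the results is to judge the effectiveness of BFR, so a clinic difference could be reported as a treatment effect.

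The matched same-clinic patients share the clinic and could throw light on this, but the plan does not settle whether they are always used, or whether they replace, supplement or are pooled with the outside controls. The no-contraindication criterion, listed for the BFR group only, adds a selection difference: a control could be someone who could not have entered the BFR group.

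**Working it through.** The plan gives no alpha, power, effect size or SD, so there is no figure of its own to reproduce. The check is first one of identifiability, then an illustration of size.

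**1. What each contrast estimates.** Coding from Study Design, the control criteria, the billing-run period and Background:

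| Group | n | BFR | In-house clinic | Study period |
|---|---|---|---|---|
| BFR | 33 | 1 | 1 | 1 |
| Outside prospective controls | 14 | 0 | 0 | 1 |
| Same-clinic retrospective controls | 20 | 0 | 1 | 0 |

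Write each group mean as μ + β·BFR + γ·clinic + τ·period. Then:

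- BFR minus outside = β + γ
- BFR minus same-clinic = β + τ
- BFR minus all 34 controls pooled = β + (14/34)γ + (20/34)τ = β + 0.41γ + 0.59τ

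Pooling mixes the two biases and removes neither.

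The rank of the design matrix agrees. With 33 + 14 patients and columns for intercept, BFR and clinic, the rank is 2 of 3. Adding the 20 same-clinic controls as a distinct group makes it 3 of 3. Adding a period column leaves it at 3 of 4. BFR and clinic are therefore separable only if calendar time has no effect.

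**2. When the same-clinic controls come in.** Study Design recruits 14 prospective controls and brings in retrospective ones if 20 cannot be obtained. Since 14 < 20, recruiting exactly to plan meets the trigger. The recruitment section and items 8 and 9 of the data-collection list carry no condition at all. These places cannot all describe the same plan.

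**3. Eligibility side by side.** Identical criteria (Target Population) conflict with the separate lists on two points: the clinic requirement, which is reversed for controls, and the contraindication criterion, which is absent for controls. The shared exclusion list does not restore the latter.

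**4. Illustrative size.** Suppose BFR does nothing and the clinic adds δ SD (assumed; the documents give no value). For 33 v 14:

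- SE = √(1/33 + 1/14) = 0.319 SD, with 33 + 14 − 2 = 45 degrees of freedom
- noncentrality = δ/0.319
- critical t = 2.014 at two-sided 0.05, and 2.690 at two-sided 0.01

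| Assumed δ | Noncentrality | Rejects at 0.05 | Rejects at 0.01 |
|---|---|---|---|
| 0 | 0 | 5.0% | 1.0% |
| 0.2 SD | 0.627 | 9.4% | 2.5% |
| 0.3 SD | 0.941 | 15.1% | 4.8% |
| 0.5 SD | 1.568 | 33.5% | 14.3% |

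The 0.01 column stands in for a multiplicity correction whose method the plan does not name. With 20 outside controls instead of 14, the rates at 0.05 are 10.6%, 18.0% and 41.0%. More outside controls therefore make a false attribution more likely.

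**The case against.** The prospective groups share a good deal: the same surgical practice, a common named ACL protocol and the same data points. With BFR in consistent in-house use since early 2019, contemporaneous patients without BFR plausibly had to come from outside. The study is called a pilot and admits sampling bias. The clinic effects above are assumptions, and the promised multiplicity correction would lower the rates. All of this stands and limits the size of the point. None of it separates clinic from BFR, and the clinic difference is not among the listed limitations.

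Three stronger readings are tempting, and the documents do not support them.

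- *The same-clinic controls are only a fallback that may never be used.* The 14/20 figures trigger them even if recruitment goes to plan, and two sections treat them as definite. What is documented is inconsistency, and silence on how they would be combined with the outside controls.
- *Using them would isolate BFR.* They come from January 2017 to January 2019, so they exchange a clinic difference for a calendar-time difference. KOOS, MARX and 12-month or later data are also not listed for them.
- *BFR should be credited only if both contrasts are significant.* Clinic and period effects can point the same way, so agreement does not exclude bias. The rule is also costly: simulating 33 v 14 and 33 v 20 with a shared BFR group and no confounding, both are significant at 0.05 in about 19% of trials for a true 0.5 SD effect, against 34% for the single 33 v 14 test.

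The effect of the contraindication criterion cannot be sized, because the list sits in an external manual.

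**Conclusion.** The point holds as a matter of design and consistency. In the prospective comparison BFR and clinic coincide completely, the planned analysis has no means of separating them, and the limitations do not say so. The status of the same-clinic controls and the claim of identical criteria each contradict other sections.

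The structural conclusion rests on the documents alone. The rates of 9%, 15% and 34% (about 2.5%, 5% and 14% at 0.01) rest on assumed clinic effects of 0.2, 0.3 and 0.5 SD, equal variances and full recruitment to 33 and 14. They show what could happen; nothing in the documents shows that a clinic effect exists, or how large it is. Confidence is medium, and the changes are worth making for a pilot because they are cheap.

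**What to change.** 1. **Control groups.** Reconcile Study Design, Identification and Recruitment, and items 7 to 9 of the data-collection list, so that the 20 matched same-clinic controls are extracted in all cases and the 14 and 20 figures agree.
2. **Analysis.** In Data Analysis, replace the single BFR versus non-BFR test with two separate, unpooled contrasts, each with a confidence interval: BFR v outside contemporaneous controls (open to clinic bias) and BFR v same-clinic 2017-2019 controls (open to calendar-time bias). Limit the second to strength, functional tests, RSI and IKDC.
3. **Interpretation.** State in Study Limitations that neither contrast alone isolates BFR, and that agreement between them supports a BFR effect without proving it. Do not add a both-significant rule.
4. **Eligibility.** Apply the no-contraindication criterion to prospective controls at screening, and to retrospective controls as far as charts allow. Correct Target Population to match the two inclusion lists, including the difference in clinic.

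The cost is some chart extraction that the plan already describes, fewer outcomes for the historical comparison, and a more cautious conclusion.

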### Exclusion criteria for study group and prospective controls:

- a. Specific exclusions
  - Patients older than 18 and younger than 12 at the time of surgery
  - Any additional diagnoses or deformity not related to knee injury that could affect knee strength
- Additional lower extremity injury at time of knee injury (e.g., ankle injury) requiring treatment Previous surgical intervention on the knee (ipsilateral and contralateral)

Patients with weight bearing restrictions for greater than two weeks after surgery due to concomitant pathology such as meniscal root/radial repair, chondral pathology, or multi-ligament pathology. Generic exclusion: "Subjects not meeting all inclusion criteria."

The exclusion of age is to ensure that the study population is old enough to complete testing on the HUMAC isokinetic dynamometer and young enough to be treated by one of our Elite Sports Medicine physicians.

The secondary diagnosis and previous knee injury exclusions are to limit the influence of other diagnoses or injuries on measured knee strength, as well as provide a more homogeneous group for comparison to past data.

### Identification, recruitment, consent and retention of subjects

### Patient Screening and Determination of Eligibility

### Pre-Screening

All potential patients undergoing ACL reconstruction at Elite Sports Medicine will be approached for participation for this study. Patients scheduled to undergo ACL reconstruction will be screened by the individuals listed on this protocol using our pre-screening documentation form. All patients undergoing ACL reconstruction undergo a pre-operative appointment.

### Identification and Recruitment:

Once identified as a potential candidate, the study purpose and protocol will be explained and a brief summary of the study will be provided at the conclusion of the pre-operative appointment. Patients must meet all the requirements of inclusion and exclusion criteria to be eligible for consent.

Consent: Consent will take place at the pre-operative visit. The patient/parent will be given a detailed description of the purpose and methodology for this study. They will have the opportunity to read the consent forms and ask any questions they may have about the research. If they agree to participate, they will be asked to sign the consent form and a copy will be provided.

If patients agree to enroll, all demographics and information listed in the protocol will be stored in a data collection sheet that is listed in the attachments. This sheet will be used to record all pertinent information for all active participants on the study and stored in a secure folder on the G drive.

Retention: Eligible patients will be required to be seen for a minimum of 90% of patient visits to be included in this study.

**Retrospective control**: Patients that will be used as part of the retrospective control will be collected using a billing run with CPT codes related to ACL reconstruction from January 2017- January 2019.

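### Consent before surgery requires criteria that can be settled only later, so who stays eligible and is analysed, in both groups, depends on events after treatment starts

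*Combined protocol and SAP*

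**What the plan says.** Under *Identification and Recruitment*, "Patients must meet all the requirements of inclusion and exclusion criteria to be eligible for consent". The consent paragraph in the same section says "Consent will take place at the pre-operative visit".

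The criteria that this rule covers include:
- for the study group, and in the same words for prospective controls: "Post-primary ACL reconstruction" and "Patient completed postoperative rehabilitation following standard protocols";
- for prospective controls only: "Patient did NOT use BFR training during their rehabilitation" and "Patient did NOT complete physical therapy at Connecticut Children's Sports Physical Therapy";
- as an exclusion in both groups: "Patients with weight bearing restrictions for greater than two weeks after surgery due to concomitant pathology".

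Four other places bear on who is counted:
- The exclusion list ends with a generic exclusion of anyone who fails an inclusion criterion.
- The *Retention* paragraph makes inclusion conditional on attending at least 90% of visits.
- *Target Population* describes patients who have already finished physical therapy at the study clinic.
- *Data Analysis* collects data on consenting patients who meet the inclusion criteria, and sets the study endpoint at 20 patients with one year of follow-up.

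The documents contain no two-step eligibility check and no analysis set made up of all consented patients. They do not say how a consented patient who later fails a criterion is counted or reported.

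**The concern.** Read literally, the consent rule cannot be followed, because no patient can show before surgery that rehabilitation has been completed. In practice some criteria must be applied later, and those criteria concern what happened during treatment.

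Completion and attendance can depend on how well a patient tolerates therapy and recovers. Removing patients on such grounds makes the remaining group unlike the one that started. That affects the primary strength and function comparisons. It also affects the third secondary aim, on tolerance and side effects of BFR, for which patients who drop out of therapy may be the most informative. The harm to the tolerance aim does not depend on what happens among controls.

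**Working it through.** The plan gives no figure on this point, and its sample size section states no effect size, SD, power or dropout rate. The check therefore sets each criterion against the time of consent. Two illustrations follow, with their assumptions marked.

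**1. When each criterion can be settled**

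| Criterion | Group | Earliest certain time |
|---|---|---|
| Age, previous knee surgery, other diagnoses | both | pre-operative visit |
| BFR contraindications | study | pre-operative visit |
| Primary reconstruction performed | both | surgery |
| Weight-bearing restriction over two weeks | both | operative findings for the cause; more than two weeks after surgery for the actual duration |
| Therapy not completed at the study clinic | controls | planned site can be foreseen; the fact is known only when therapy ends |
| No BFR used | controls | end of rehabilitation |
| Rehabilitation completed | both | end of rehabilitation, which *Background* says can take up to 12 months |
| At least 90% of visits attended | all eligible patients | end of the visits counted |

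Several criteria, though not all, fall after consent. *Study Design/Procedures* starts therapy about 2 to 5 days after surgery, and *Proposed Protocol* begins BFR in weeks 1 to 2. The actual length of a weight-bearing restriction would therefore be known only after BFR had begun.

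**2. What the 90% rule could do (illustration)**

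The documents do not give the total number of visits. Assume that the rule applies to the BFR sessions alone: 2 per week x 12 weeks = 24. Then 0.9 x 24 = 21.6, so 22 sessions are needed and at most 2 may be missed. With independent attendance at probability p per session, the chance of staying included is P(X >= 22), where X is Binomial(24, p):

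| p (assumed) | Chance of staying included | Expected number of 33 |
|---|---|---|
| 0.85 | 0.280 | 9.2 |
| 0.90 | 0.564 | 18.6 |
| 0.95 | 0.884 | 29.2 |
| 0.98 | 0.988 | 32.6 |

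Under these assumptions the rule could remove almost nobody or most of the group.

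**3. Effect on a mean and on the difference (illustration)**

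Let s be the share of a group removed, and d the shortfall of those removed relative to those kept, in SD units. The full-group mean lies s x d below the mean of those kept, so removal raises the group mean by s x d.

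- s = 0.10, d = 0.5: 0.10 x 0.5 = 0.05 SD
- s = 0.20, d = 1.0: 0.20 x 1.0 = 0.20 SD

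In the BFR group these shares are 0.10 x 33 = 3.3 and 0.20 x 33 = 6.6 patients, or about 3 to 7.

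The bias in the difference (BFR minus control) is s_B x d_B - s_C x d_C:
- controls not selected: +0.05 to +0.20 SD;
- equal selection in both groups: 0;
- BFR at the lower case and controls at the upper: 0.05 - 0.20 = -0.15 SD.

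The sign is therefore open. For scale, the standard error of a difference between 33 and 14 patients is sqrt(1/33 + 1/14) = 0.32 SD.

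**The case against.** The strongest reply is that the conflict is only loose tense. Screening and consent concern patients scheduled for surgery, so the past-tense criteria may mean planned rehabilitation and planned non-use of BFR. That reading is reasonable and removes part of the conflict. It does not remove the 90% attendance rule, which can only be applied after treatment, and it sits poorly with *Target Population*.

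A reader might infer three stronger claims that the documents do not support:
- *Patients who stop BFR become ineligible, which flatters BFR.* The criterion concerns rehabilitation under standard protocols, and the protocol describes BFR as an addition to these. A patient who stops BFR but finishes standard rehabilitation still meets it. *Proposed Protocol* records whether each session could be completed, together with side effects, and nothing there removes a patient for stopping. Controls carry the same completion criterion, so the direction is not shown.
- *The study group is chosen after treatment.* Patients are screened and consented before surgery, and group follows mainly from where therapy takes place, which may be foreseen. What is settled later is who stays eligible and is analysed.
- *The plan presents 33 and 14 as the numbers analysed.* These are recruitment figures, and *Data Analysis* sets its endpoint at 20 patients with one-year follow-up.

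It also stands that even 0.20 SD is smaller than the 0.32 SD standard error at 33 against 14. But that error is random, whereas selection can shift the estimate systematically.

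**Conclusion.** The point holds as a conflict in the current text. Consent timing cannot be reconciled with the completion, BFR non-use and weight-bearing criteria as written. Together with the 90% rule, they make eligibility and analysis in both groups depend on events after treatment starts.

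Neither the size nor the direction of the bias can be computed from the documents. The 0.05 to 0.20 SD figure is a shift in one group's mean and rests on assumed removal shares and shortfalls. It becomes bias in the difference only if the other group is not similarly selected. Equal selection cannot be assumed either: prospective controls are treated at outside facilities, and the documents do not say how their completion or attendance is verified. The risk to the tolerance aim stands whatever happens in the control group.

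**What to change.** Stage the criteria and define the analysis sets.

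1. **At consent.** List the criteria that are checked at the pre-operative visit. Let planned therapy site and planned BFR use or non-use define the group.
2. **After surgery, before the first therapy session.** Confirm the surgical criteria from the operative record, and count failures as screen failures. The study team must reconcile the timing of the weight-bearing criterion with the consent rule.
3. **Out of eligibility.** Remove completion of rehabilitation, actual non-use of BFR and 90% attendance from *Target Population*, both inclusion lists and the *Retention* paragraph. Use them only to define a secondary per-protocol set. If the attendance rule stayed, selection on adherence would remain even with the completion criterion gone.
4. **Main analysis.** Include all consented patients who pass steps 1 and 2, in the group in which they started. Report every post-consent exclusion by group and reason.

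The cost is protocol wording, with no new visits or measurements. The downside is that the main analysis will include some patients with incomplete treatment, so the estimated effect may be slightly smaller.
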